**(Table 1)**

Figure 1: Normed percentile transformation of AMH Values

[figure not shown]

Table 1: Estimated values of AMH differences based on normed percentile transformation

AMH Differences (pmol/L)		
	Treatment Group	Control Group
Mean	17.06	3.57
Standard Deviation (SD)	22.28	4.31
Coefficient of variation (CV) =(SD/Mean)	1.31	1.21
Number of participants	5	100

Using the pilot data, the investigators anticipate that 32 participants will be required to demonstrate a differential AMH level. (**Table 2**)

Table 2: Power Calculation

Sample Size Calculation		
	Treatment Group	Control Group
Mean (pilot)	17.06	3.57
Standard Deviation SD (pilot)	22.28	4.31
Standard Error (S.E)	6.18	1.08
Lower CI	4.70	1.42
Upper CI	29.42	5.73
Minimum (n)	11	11
Small sample margin	2	2
Attrition (assumed)	3	3
Total (n)	16	16

The minimum sample size is 11 participants. Considering the small size of the pilot and the very low risks thus far, the investigators include 2 more observations to boost power, and assume an attrition rate of approximately 25%. This leads to a total (n) of 16 participants per arm, with a power of 0.95 to detect a difference at the 5% level using a standard t-test on the log-transformed difference in means of AMH, the robust proxy for fertility. It will be necessary to perform an interim analysis given the low number of participants available for the power calculation.

With regards to further data analysis of the study, the investigators plan to use descriptive statistics (mean +/- standard deviation), two-sided tests, and Wilcoxon rank sum test to compare continuous variables in two groups. For more than two groups, the Kruskal-Wallis exact test will be used. For comparing a proportion with an expected value, a binomial exact test will be used. Results are considered significant at  $p<0.05$ . Analysis will be performed with SAS (version 9.2) and Statistical Package for Social Sciences for Windows (version 16). Statistical analysis will be performed under the supervision of [name].

Data and all appropriate documentation will be stored for a minimum of 10 years after the completion of the study, including the follow-up period.

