### *Data Collection*

The investigators will collect the following data: patient demographics including age, BMI, gravida, parity and gynaecological surgical history. Pre-operative data will include findings from the diagnostic transvaginal scan and measure of ovarian reserve: AMH and AFC. Intra-operative data will include transvaginal findings during surgery (in the experimental group only), such as cyst location and size or any new lesions noted. Residual ovarian volume post cystectomy will also be measured intraoperatively. Histology data will include the histological diagnosis of the ovarian cyst and volume of normal ovarian tissue excised during the cystectomy measured as per margins in mm. Outcomes following surgery including duration of surgery (mins), length of hospital stay (days) and post op complications will be recorded.

Post operatively, participants will return to clinic for follow up at 3 and 6 months post -surgery, whereby a blood test will be taken to assess ovarian reserve by measuring the AMH level. The outpatient gynaecology nurse in clinic or research staff will be responsible for taking the blood sample

and will only require one EDTA bottle (yellow top) to be filled (20-40mls). The blood samples will be processed by Imperial College Healthcare Trust laboratories or University College London Hospitals NHS Foundation Trust, depending on the site taken, and will be discarded as per local protocol once the AMH has been determined. There are no specific storage or transfer requirements outside of normal practice. Therefore, samples will be ‘podded’ to the labs once taken in the usual way. In addition, an ultrasound will be performed during the follow up appointment to measure AFC and assess volume of preserved ovarian tissue. Follow up appointments should take approximately 20 minutes. The two blood tests and two ultrasound scans carried out during the follow up process are considered standard clinical practice, and therefore not considered additional investigations for the purpose of this research study.

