### 3.1 STUDY OUTCOME MEASURES

Primary: AMH and AFC measurements at 3 and 6 months post-surgery.

Secondary: Surgical outcomes including:

- Duration of surgical procedure (minutes),
- Duration of hospital stay (days)
- Presence of intra-operative cyst rupture or spillage (Yes/No)

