**Please send SAE forms to: [[contact]](mailto:[contact])**

**[contact] (Mon to Fri 09.00 – 17.00)**

## 6.0 ASSESSMENT AND FOLLOW-UP

Follow up appointments at 3 and 6 months post -surgery will be carried out at the participants' respective hospital gynecology clinic responsible for the care and management of the ovarian cyst. During this appointment, the responsible physician will assess recovery post- surgery and perform a clinical assessment. A blood test to measure ovarian reserve including assessment of AMH will be taken by the outpatient gynaecology nurse or research staff assigned to the clinic. A transvaginal ultrasound scan will be performed during the appointment by an experienced gynaecology specialist trainee or Consultant to assess the AFC and preserved ovarian volume of tissue remaining. Any incidental findings identified on ultrasound scan of gynaecological pathology, will be managed by the responsible clinician and the participants GP will be informed by letter.

The majority of participants are likely to be discharged following the 2nd clinic appointment 6 months post- surgery, whereby no further involvement is required in the study. If a participant becomes pregnant during the follow up period, follow up will be deferred to 3 and 6 months post completion of pregnancy.

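### AMH at 3 and 6 months is primary, but the SAP names only single-visit two-group tests and fixes neither the visit tested nor the handling of missing values

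*SAP*

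**What the plan says.** Section 3.1 gives as the primary outcome "AMH and AFC measurements at 3 and 6 months post-surgery" and ranks neither visit above the other. Baseline is collected too (section 3.0, Data Collection): "Pre-operative data will include findings from the diagnostic transvaginal scan and measure of ovarian reserve: AMH and AFC". Each woman can therefore contribute one AMH value before surgery and two after it.

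Section 7.0 states power for a comparison "using a standard t-test on the log-transformed difference in means of AMH". For further analysis it lists "two-sided tests, and Wilcoxon rank sum test to compare continuous variables in two groups". It adds a Kruskal-Wallis test for more than two groups and a binomial test for a proportion, neither of which bears on a two-arm AMH comparison.

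On loss, section 7.0 says that the investigators "assume an attrition rate of approximately 25" per cent, and Table 2 adds 3 women per arm for it. The SAP gives no rule for missing values, no model that uses the two visits together and no sensitivity analysis.

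The planning data for both arms, in the opening paragraphs of section 7.0, are 3-month data.

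**The concern.** A t-test or rank sum test takes one value per woman. Applied at 6 months, it leaves out a woman who has no 6-month value, even when her 3-month value is in the database and is correlated with the missing one. Two things are at stake.

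- **Precision.** The 3-month value carries information about the 6-month mean that a single-visit test cannot use.
- **Bias.** If leaving is linked to the 3-month AMH, the women who return are a selected group. The trial is open, and of the follow-up tests the SAP says: "The two blood tests and two ultrasound scans carried out during the follow up process are considered standard clinical practice". The 3-month result can therefore be known before the 6-month visit. Section 6.0 also postpones follow-up for women who conceive, which is another route to late or absent 6-month values. Extra recruits replace lost numbers but do nothing about selective loss.

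**Working it through.** **Inputs from the SAP (section 7.0, Tables 1 and 2).** Means 17.06 and 3.57 pmol/L; SDs 22.28 and 4.31; power 0.95; 5% level, two-sided; minimum 11 per arm, plus 2, plus 3 for attrition, giving 16.

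**Inputs not in the SAP (assumed).** The 3-to-6-month correlation ρ of log AMH; that all loss falls between the two visits; and, for bias, how strongly leaving depends on the 3-month value.

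**Step 1: reproduce the plan's figure.** The power sentence is read as a two-sample t-test on log AMH. With SD_log = √ln(1 + CV²), the arms have 0.998 and 0.948, root mean square 0.973. The difference in log means is (ln 17.06 − 0.998²/2) − (ln 3.57 − 0.948²/2) = 1.516. Then

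n = 2 × (1.960 + 1.645)² × 0.973² / 1.516² = 10.7, so 11 per arm.

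Using ln(17.06/3.57) = 1.564 instead gives 10.06, again 11. The stated minimum reproduces.

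**Step 2: power of a 6-month t-test after loss.** The text's 25% of 16 is 4 lost, leaving 12. Table 2 budgets 3 (3/16 = 18.75%), leaving 13. Exact (noncentral t) power with effect 1.516 and SD 0.973 is 0.954 with 12 per arm and 0.968 with 13.

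**Step 3: what the 3-month values add under random loss.** With n randomised and n_c completing per arm, the variance of the 6-month mean under a two-visit likelihood analysis, relative to completers only, is 1 − ρ²(n − n_c)/n. The effective sample size is n_c divided by that ratio.

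| Lost per arm | ρ | Variance reduction | SE reduction | Power, completers → two-visit |
|---|---|---|---|---|
| 3 of 16 | 0.7 | 9.2% | 4.7% | 0.968 → 0.980 |
| 3 of 16 | 0.8 | 12.0% | 6.2% | 0.968 → 0.983 |
| 3 of 16 | 0.9 | 15.2% | 7.9% | 0.968 → 0.986 |
| 4 of 16 | 0.7 | 12.3% | 6.3% | 0.954 → 0.975 |
| 4 of 16 | 0.8 | 16.0% | 8.3% | 0.954 → 0.980 |
| 4 of 16 | 0.9 | 20.3% | 10.7% | 0.954 → 0.985 |

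A simulation at trial size (16 per arm, 4 lost, log SD 0.975, 6,000 trials per scenario) gave variance ratios of 0.886, 0.840 and 0.805 for ρ = 0.7, 0.8 and 0.9. Those are reductions of 11%, 16% and 20%, in line with the formula. At ρ = 0.5 the SE falls by only 2.4% (3 lost) or 3.2% (4 lost).

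**Step 4: bias when leaving depends on the 3-month value.** Large-sample simulation with log SD 0.973; where low values prompt leaving, the odds of leaving triple per SD lower 3-month log AMH (assumed). Negative values run against UGLOC.

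| Drop-out pattern | True effect (log) | Loss, control / UGLOC | Completers' bias at ρ = 0.5 / 0.8 / 0.9 |
|---|---|---|---|
| Low values leave, control arm only | 0 or 1.516 | 25% / 25% | −0.11 / −0.18 / −0.20 |
| Low values leave, both arms alike | 1.516 | 45% / 17% | −0.12 / −0.19 / −0.21 |
| Low values leave, both arms alike | 0 | 29% / 29% | about 0 |

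The two-visit likelihood estimate had bias of at most 0.003 in every row. In the second row total loss is about 31%, above the plan's 25%. A trial-size simulation with weaker dependence in the control arm (odds multiplied by 1.6 to 2.7) gave completers' AMH ratios of 0.82 to 0.91 times the truth, that is −0.20 to −0.09 in logs.

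**The case against.** A reader might infer that the plan discards women lost before 6 months and tests whoever has a value. The SAP does not say so. The t-test appears in the sample-size sentence, and powering on a t-test does not settle how missing values are treated. No visit is attached to it, and both planning datasets are 3-month data; a 3-month t-test would keep every woman lost later. Omission is the default behaviour of the named tests at 6 months, not a stated rule.

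The sizes also rest on assumptions. The SAP does not say when the loss occurs, and Table 2 allows for 3 lost per arm, not 4. Neither ρ nor any link between AMH and leaving is documented. A low 3-month result could equally encourage a woman to return, and section 6.0 expects most women to be discharged only after the 6-month appointment, which favours attendance. On the plan's own inputs the t-test already meets its 95% target with 12 or 13 women per arm.

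All of this stands, and it limits the point to a modest one. It does not close the gap: 6 months is primary on the same footing as 3 months, no named test can use both visits, and recruiting extra women does not address selective loss.

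**Conclusion.** The point holds as a gap in the specification with an inexpensive improvement available. The SAP does not fix the primary visit or the handling of missing AMH, and the tests it names would by default leave out known 3-month data in a 6-month comparison.

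The precision gain is modest: one to three points of power for ρ between 0.7 and 0.9, with all loss falling after the 3-month visit. Bias is the better reason to change. Under the two unfavourable patterns examined it is roughly 0.1 to 0.2 log units, about 7–13% of the planned 1.516 (0.1/1.516 and 0.2/1.516), and it runs against UGLOC. It is about 0 when the pattern is the same in both arms and there is no treatment effect. These figures show what could happen under assumed drop-out; they do not predict what the plan will produce, and the documents do not show that such drop-out will occur.

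**What to change.** - Name one primary time point for AMH.
- Analyse log AMH at 3 and 6 months in one mixed model for repeated measures with arm, visit, arm-by-visit interaction and baseline log AMH, an unstructured within-woman covariance and Kenward-Roger degrees of freedom. Include every randomised woman with at least one post-operative value, and take the primary contrast at the named visit.
- Keep the per-visit t-test as a sensitivity analysis, and add one that allows for data not missing at random.
- Treat AFC in the same way on a suitable scale.
- Settle the wording before any comparative analysis, including the interim analysis that section 7.0 calls for.

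The cost is SAP wording and a standard model in SAS, which the plan already names; no new data or visits are needed. The downside is reliance on a missing-at-random assumption. The model also does not help with women lost before the 3-month visit, who have no post-operative value to contribute.

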## 1.3 RESEARCH QUESTION

The primary objective of this study is to determine the efficacy of intraoperative ultrasound-guided ovarian cystectomy (UGLOC) for the management of benign ovarian cysts as an adjunct of fertility sparing surgery. This will be determined through assessment of post-operative AMH and AFC, which are both reliable measures of ovarian reserve. The secondary objective is to determine the surgical outcomes in women who have undergone intraoperative ultrasound guided ovarian cystectomy and compare this to the control group.

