## 7.0 STATISTICS AND DATA ANALYSIS

A study by Kwon et al investigated the impact of laparoscopic ovarian cystectomy for benign cysts on post-operative ovarian reserve, as measured by follow up AMH levels taken 3 months after surgery. This particular study is considered to be most applicable for determining the power calculation of our proposed randomised controlled trial based on the following principles: pathology of the ovarian cysts were benign in nature and the sample size of the paper is one of the largest reported in the literature review.

From a sample size of 100 women, this paper deduced that AMH levels decreased on average 30.58% (+/-29.66%) between the pre-operative value to the level assessed 3 months following surgery. Specifically, the group of participants who underwent laparoscopic ovarian cystectomy for benign ovarian pathology had a mean (+/-SD) serum AMH of 1.59 (+/- 1.92)(ng/ml), which when converted to (pmol/L) is 3.57 (+/-4.31).

At present there are no reported studies assessing the change in AMH levels following ultrasound guided ovarian cystectomy. However, the investigators of this study have performed a small number of ultrasound-guided surgeries on 5 women, and therefore have a small data set, which can be considered a *pilot* study.

Amongst 5 women who have undergone ultrasound guided laparoscopic ovarian cystectomy, the mean difference (+/-SD) in AMH levels measured 3 months post operatively from pre-op levels is: 14.46 (+/- 21.02) pmol/L. This represents a substantial clinical difference according to previous research, and would imply women being less likely to experience fertility issues as they would be near the lower end of the normal range of AMH rather than in the lowest decile (ca. 0-4.5).

In order to calculate the sample size, the investigators have leveraged the pilot data to derive an estimate of the mean and standard deviation. From the literature, it can be assumed AMH is approximately log-normally distributed, as demonstrated from figure 1. Using this figure, the investigators have determined the normed (percentile) transformation of values from the pilot study.

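### The primary AMH variable is stated both as a post-operative level and as a change from pre-op, and on the most natural reading the collected pre-op AMH goes unused

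*SAP*

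**What the plan says.** The outcome definitions point to a level. Section 1.3 says of efficacy: "This will be determined through assessment of post-operative AMH and AFC". Section 3.1 lists "AMH and AFC measurements at 3 and 6 months post-surgery". The sample-size statement in section 7.0 says that "32 participants will be required to demonstrate a differential AMH level".

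The sample-size inputs in section 7.0 point in two directions:

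- **Pilot (5 women).** The mean difference "in AMH levels measured 3 months post operatively from pre-op levels is: 14.46" pmol/L. The next sentence reads this figure as a level, saying of the women that "they would be near the lower end of the normal range of AMH rather than in the lowest decile".
- **Control (published cohort).** The women "who underwent laparoscopic ovarian cystectomy for benign ovarian pathology had a mean (+/-SD) serum AMH of 1.59" ng/ml, which the plan converts to 3.57 pmol/L. This is a level.
- **Table 1.** Its title is "Estimated values of AMH differences based on normed percentile transformation", and both columns (17.06 and 3.57 pmol/L) stand under a heading that calls them differences.

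The test is named once, in the power sentence after Table 2: "a standard t-test on the log-transformed difference in means of AMH". The next paragraph, on further data analysis, gives a Wilcoxon rule for continuous variables and does not say whether it covers AMH. Section 3.0 (Data Collection) and Appendix 1 show that AMH is measured before surgery, but section 7.0 states no change score, ratio to baseline or covariate.

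**The concern.** The primary analysis should be readable in only one way before data are seen. That matters more here because the trial is unblinded and section 7.0 foresees an interim analysis. As written, one analyst could compare log post-operative levels and another could compare changes, and both could cite section 7.0.

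Two things are at stake. First, the stated n and power compare something described as a change in one arm with a level in the other. Second, if the level is meant, the plan leaves out the covariate likely to help most. AMH varies widely between women (CVs of 1.21 and 1.31 in Table 1) and only about 13 women per arm are expected to be analysed, so the estimate will be imprecise and exposed to chance baseline imbalance.

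**Working it through.** **1. Reproduce the plan's n.** Inputs from Tables 1 and 2: means 17.06 and 3.57, SDs 22.28 and 4.31, power 0.95, 5% level (two-sided, as the further-analysis paragraph has it).

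- Log SD = √ln(1 + (SD/mean)²): treatment 0.998, control 0.948, pooled 0.973.
- Log-mean = ln(mean) − (log variance)/2: treatment 2.339, control 0.823. The difference is 1.516, a ratio of 4.55.
- n per arm = 2(1.960 + 1.645)² × 0.973² / 1.516² = 10.7, so 11, as in Table 2.
- Exact t power at a difference of 1.516: 0.935 with 11 per arm, 0.968 with 13.

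So a log scale was used, with between-patient variation only and no pre/post correlation. The arithmetic is the same whatever the columns are called, so it does not show which variable was meant.

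**2. Can the control 3.57 be a change?** Section 7.0 gives an average fall of 30.58%. Applied roughly to the mean:

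- if 3.57 is the post-op mean, the fall is 3.57/0.6942 − 3.57 = 1.57 pmol/L;
- if 3.57 is the pre-op mean, the fall is 3.57 × 0.3058 = 1.09 pmol/L.

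Neither is 3.57, so the control column is a level, as the text says. The text describes the pilot figure as a difference.

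**3. Which reading can be carried out?** Raw changes of opposite sign cannot all be logged, and the plan expects AMH to fall on average in controls. A log post-operative level can always be formed and matches sections 1.3 and 3.1. That makes it the most natural reading, and it does not use pre-op AMH.

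**4. What adjustment would buy.** Settings: 13 per arm (16 minus the 3 assumed lost); log SD 0.973 both before and after surgery. The documents do not give the pre/post correlation, so it is varied. The CI factor is exp(median 95% half-width). ANCOVA results come from 100,000 simulated trials per correlation; unadjusted power and detectable ratio come from the noncentral t.

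| Analysis (assumed log correlation) | 95% CI factor | Ratio detectable at 80% power | Power if true ratio is 2 (assumed) |
|---|---|---|---|
| Unadjusted t-test | 2.17 | 3.05 | 0.41 |
| ANCOVA (0) | 2.21 | 3.1 | 0.40 |
| ANCOVA (0.5) | 1.99 | 2.7 | 0.50 |
| ANCOVA (0.7) | 1.76 | 2.3 | 0.67 |
| ANCOVA (0.9) | 1.41 | 1.6 | 0.97 |

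**5. Chance imbalance.** The SE of the difference in mean log pre-op AMH is 0.973 × √(2/13) = 0.382. The probability that the arms differ at least 1.5-fold is P(|Z| > ln 1.5 / 0.382) = P(|Z| > 1.06) = 0.29.

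**6. The choice of variable changes n.** Suppose percent change were the variable, with the plan's control fall of 30.58% and SD of 29.66 points (same SD assumed in both arms). Even if ultrasound guidance prevented all decline, power 0.95 would need 26 per arm by exact t, and 13 per arm would give 0.71.

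**The case against.** The strongest reply is that the outcome definition itself is stable. The study summary and sections 1.3 and 3.1 all give post-operative AMH, so the conflict lies in the sample-size inputs and one loose phrase. That is largely right about where the conflict lies. But the loose phrase is the only statement of the AMH test, so the conflict reaches the analysis as well.

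A second reply is that the phrase could mean a change on the log scale, log(post) minus log(pre), which can be computed for any positive AMH and does use the pre-op value. The plan does not state this. It also fits poorly with inputs in pmol/L and with an n that reproduces from between-patient CVs alone. On that reading the CI factor would be 2.17, 1.83 or 1.42 at correlations 0.5, 0.7 or 0.9, against 1.99, 1.76 or 1.41 for ANCOVA. The gain from ANCOVA then nearly vanishes at high correlation, but ANCOVA is no less precise at any of these values.

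Three further points stand as limits:

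- An unadjusted comparison is valid under randomisation, and at the plan's own implied effect its power with 13 per arm is already about 0.97. That effect, however, comes from the mismatched inputs and five pilot women.
- The pilot figure moves from 14.46 to 17.06 through a percentile transformation based on a figure not available here. What 17.06 represents cannot be checked, and the pooled SD of 0.973 inherits that doubt.
- The Wilcoxon paragraph opens as further analysis and can fairly be read as not covering AMH. That part of the point is minor.

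**Conclusion.** The concern holds and should be fixed before outcome data are seen. The inconsistency is explicit in the text: the outcome is defined as a level, the pilot input is described as a change, the control input is a level, and Table 1 labels both as differences. The stated n and power therefore lack a common basis, even though 11 per arm reproduces arithmetically.

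The statement that pre-op AMH goes unused depends on reading the test as one on log post-operative level. That is the most natural reading but not the only possible one. On it, adjustment would narrow the CI factor from about 2.17 to between 1.99 and 1.41 for correlations of 0.5 to 0.9. The benefit is in precision and in power for effects smaller than the 4.55-fold ratio implied by Table 1. The correlations, the two-fold ratio and the pre-op log SD are assumptions.

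**What to change.** In section 7.0:

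- Name one primary AMH analysis: ANCOVA of log post-operative AMH on arm and log pre-op AMH, reported as a ratio of geometric means with 95% CI.
- Name the primary visit. The sample-size inputs are described at 3 months, but section 3.1 lists 3 and 6 months, so the sponsor should confirm.
- Analyse AFC with its pre-op value as covariate.
- State that Wilcoxon is a sensitivity analysis for AMH and the general rule for other continuous variables.
- Re-derive both columns of Table 1 as the same quantity from the pilot and control data, then restate n and power. Changing the column label is not enough, because it cannot turn a change into a level.

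The analysis change costs wording and one degree of freedom. It needs no new data, since pre-op AMH and AFC are already collected, and if pre-op AMH proved uninformative the CI factor would widen only from 2.17 to 2.21. Re-deriving Table 1 takes work on the existing data and may change the stated sample size.

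### AFC is a primary measure with a pre-operative count on record, but the only test in Section 7.0 that reaches it makes no baseline adjustment and gives up precision

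*SAP*

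**What the plan says.** Section 3.1 sets the outcome: "Primary: AMH and AFC measurements at 3 and 6 months post-surgery". AFC therefore stands beside AMH as a primary measure.

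Section 3.0, Data Collection, covers both ends of the comparison. Before surgery: "Pre-operative data will include findings from the diagnostic transvaginal scan and measure of ovarian reserve: AMH and AFC". After surgery, "an ultrasound will be performed during the follow up appointment to measure AFC". Appendix 1 schedules a transvaginal ultrasound before treatment and at months 3 and 6.

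Section 7.0 gives two methods that could serve a two-group comparison of a continuous measure. The first belongs to the sample size and is tied to AMH: "using a standard t-test on the log-transformed difference in means of AMH". The second is general and comes in the paragraph after Table 2. It lists descriptive statistics, "two-sided tests" and the "Wilcoxon rank sum test to compare continuous variables in two groups". That sentence does not name AFC. The section contains no regression, analysis of covariance or baseline covariate, and does not define the AFC variable as a follow-up value or a change.

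**The concern.** Follicle counts are likely to differ widely between women aged 18 to 50 before any surgery. If follow-up counts are compared without the pre-operative count, all of that starting variation stays in the error term. AFC also has no sample-size calculation of its own: the 16 per arm in Table 2 rests on AMH alone. Its power therefore depends on how efficiently it is analysed, and the plan leaves out a covariate that the trial already records. Because the AFC variable is undefined, the choice between follow-up count and change could also be made after the data are seen.

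**Working it through.** **The plan's own figure.** The only stated sample size is 11 per arm for AMH, "with a power of 0.95 to detect a difference at the 5% level". From Table 1:
- Log-scale SD = sqrt(ln(1 + CV²)), with CV = 22.28/17.06 and 4.31/3.57. This gives 0.998 and 0.948, root mean square 0.973.
- Log difference = ln(17.06/3.57) = 1.564, or 1.516 as the difference of log-scale means.
- n = 2 × (1.960 + 1.645)² × 0.973² / difference² = 10.1 or 10.7, so 11 per arm either way.

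The figure reproduces. It concerns AMH and says nothing about power for AFC.

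**Inputs for AFC.** Evaluable women per arm: 13 (Table 2: 11 + 2, before the 3 added for attrition). Test level: two-sided 5%. The SAP gives no AFC SD, effect or correlation r between pre-operative and follow-up counts. Assumed here: a 1 SD effect, and r = 0.3, 0.5 and 0.7.

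**Variance.** Relative to an unadjusted comparison of means, analysis of covariance (ANCOVA) has variance (1 − r²) × [1 + 1/(N − 4)]. The second factor is the small-sample cost of estimating the slope. With N = 26 it is 1 + 1/22 = 1.045.
- r = 0.3: 0.91 × 1.045 = 0.95
- r = 0.5: 0.75 × 1.045 = 0.78
- r = 0.7: 0.51 × 1.045 = 0.53

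Break-even is where 1 − r² = 1/1.045, that is, r of about 0.2. Below that, adjustment gains nothing.

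**Power by simulation** (13 per arm, 1 SD effect). Normal data and integer counts with an assumed mean of 10 and SD of 5 gave nearly the same results for the rank-sum test and ANCOVA.

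| Analysis of AFC | r = 0.3 | r = 0.5 | r = 0.7 |
|---|---|---|---|
| Rank-sum, follow-up count | 0.64-0.66 | 0.64-0.66 | 0.64-0.66 |
| t-test, follow-up count | 0.68-0.69 | 0.68-0.69 | 0.68-0.69 |
| Rank-sum, change | 0.50 | 0.65 | 0.85 |
| Rank-based ANCOVA | 0.68 | 0.75 | 0.87 |
| ANCOVA | 0.70 | 0.79 | 0.91 |

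Type I error was close to 5%, or slightly below it for the rank-sum test. With all 16 per arm evaluable, the rank-sum test on follow-up counts gives about 0.75, and ANCOVA 0.81, 0.87 and 0.97.

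**Separating the two changes.** Moving from rank-sum to ANCOVA changes the test and also adds the covariate. The t-test row isolates the covariate. At r = 0.3 it adds only a point or two (0.68-0.69 to 0.70), so most of the gain there comes from leaving the rank test. At r = 0.5 it adds about 10 points, and at r = 0.7 about 22.

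**The case against.** The strongest objection is that the plan commits no error of validity. The rank-sum test holds its level in a randomised comparison. A reader might infer that chance imbalance in baseline AFC biases the unadjusted result. Such imbalance will occur: the baseline difference has a standard error of sqrt(2/13) = 0.39 SD, so a gap of 0.5 SD or more arises about 20% of the time. But that variation is already in the test's error. Counting it as a separate harm counts the same variance twice, and nothing in the SAP supports a claim of bias.

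Three further objections stand in part.
- **The test reaches AFC only by inference.** A reader might take the SAP to assign an unadjusted Wilcoxon test of follow-up counts to AFC. It does not say so. Section 3.1 reads like a follow-up value, but Section 7.0 describes the pilot AMH result as a difference from pre-operative levels. A rank-sum test on change in AFC would fit the text and would use the baseline. It would still have less power than ANCOVA throughout, and at r = 0.3 less than ignoring baseline.
- **The gain rests on assumed inputs.** The correlation may be low: the pre-operative count is made with the cyst in place, Section 4.2 does not exclude delayed surgery, and Section 6.0 allows different grades of operator at follow-up.
- **Not every woman is certain to have a comparable baseline count.** Section 4.2 admits women scanned only transabdominally, to be analysed separately, and the list of data items does not guarantee completeness. A simple ANCOVA would drop women without a baseline, whereas a rank-sum test on follow-up counts would keep them.

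**Conclusion.** The point holds as one of efficiency and incomplete specification. A primary measure with a recorded baseline is left to a general sentence that names neither the AFC variable nor a baseline term.

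With 13 evaluable per arm and a 1 SD effect, prespecified ANCOVA raises power from about 0.64-0.66 to 0.70, 0.79 or 0.91 at r = 0.3, 0.5 or 0.7. The part due to adjustment itself is small at r = 0.3 and absent at about 0.2 or below. These figures rest on an assumed r, SD and effect, and are for AFC on its untransformed scale. They show the order of the loss, not its value in this trial. The recommendation does not depend on which AFC variable was intended, since ANCOVA has more power than the rank-sum test on either one across the range shown.

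**What to change.** In Section 7.0:
- Name AFC at follow-up as the variable, at 3 and at 6 months.
- Prespecify one model: analysis of covariance of AFC on arm and pre-operative AFC. Fix a single scale in advance for both counts, for example the square root, so that it is not chosen after looking at the distribution.
- Report the adjusted difference with its 95% CI.
- Keep the Wilcoxon rank-sum test on follow-up AFC as a sensitivity analysis.
- State a simple rule for women without a baseline count, such as imputing the baseline mean, so that they are not dropped.

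Use pre-operative AFC as a covariate rather than subtracting it, because a change score would carry the error of a count made with the cyst in place in full.

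The cost is a few sentences of SAP text and one degree of freedom. No extra women, visits or measurements are needed.
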